The miniplate and screw system for maxillofacial fractures that are widely used and available at Cipto Mangunkusumo Hospital are Biomet® and Osteomed®. Both brands are imported and similar in their quality. These brands, however, are very costly due to the importing expenses and luxury goods additional tax. Based on government law number 42, 2009, Chapter 5, imported medical devices are considered as luxury goods and will be charged with selling tax up to a minimum of 10 percent. Moreover, BPJS as national healthcare insurance in Indonesia comes to a serious deficit, therefore they demand the hospital to be more careful on patient management. In our hospital, through a division of "Kendali Mutu Kendali Biaya" (KMKB), they control the application of every medical implant, an expensive drug used and other expensive procedure.

A locally-made miniplate and screw as internal fixators for maxillofacial fracture have been studied before on an animal. Previously conducted animal study the local miniplate and screw did not produce any wound complication with respect of infection, seroma, and hematoma during observation and the bone is healed according to the timeline.³³ Moreover, local miniplate and screw fixation allow a not-inferior bone healing compared to import one in terms of bone density, muscle density, and peri-implant bone density.³⁴ Furthermore, this locally-made miniplate and screw needs to face greater force and more complex system in the human body. Therefore, we will use it in patients with maxillofacial fractures, to evaluate the locally-made miniplate and screw efficacy while also reducing the cost that has to expend by our national health insurance.

As stated in The Ministry of Health Regulations number 86, 2003 regarding The Road Map Development of Medical Equipment Industry, Ministry of Health demands local medical products to grow faster. On the contrary, medical devices currently available in Indonesia could not provide the demand for medical products. Ninety percent of medical products that are distributed in Indonesia are imported. In the globalization era, many products enter Indonesia easily, while the supply could not meet the demand, causing the price of these medical products

increases every year. As a result, the need for healthcare service and medical products supply does not meet.¹⁰

Also addressing to the new national healthcare system number 27, 2014 regarding Technical Instructions System of Indonesian Case Base Groups, where medical coverage is not based on medical expenses but the grouping of diagnoses and treatment based on ICD-9, the high cost of medical products often complicate the hospital policy.¹¹

Therefore, as suggested by the Indonesian Ministry of Health, we are going to use our local plate and screw for maxillofacial fractures management to answer the balance of supply and demand of local medical products. On the other hand, it could help the government to reduce medical expenses.

Aim Of The Study

The aim of this experiment is to investigate the usage of the locally-made miniplate and screw are not inferior compared to the existing benchmark miniplate and screw in terms of bone healing, surrounding tissue reactions, and screw loosening.

Study Hypothesis

The locally-made miniplate and screw are not-inferior compared to the existing benchmark miniplate and screw in terms of bone healing, surrounding tissue reactions, and screw loosening.

OBJECTIVES AND OUTCOMES

Primary Objective

To evaluate bone density radiologically (in Houndsfield Unit) after plate and screw fixation with locally-made compared to existing benchmark miniplate and screw

Secondary Objective

- To evaluate if there is any loosening screw following both locally-made and existing benchmark miniplate and screw fixation.
- To evaluate if there is any sign of local tissue reaction following both locally- made and existing benchmark miniplate and screw fixation.

STUDY DESCRIPTION

Research Design

This study will be performed on patients with maxillofacial fractures. The study is a blind randomized clinical study comparing locally-made titanium plate and screws with the existing benchmark, BIOMET® miniplate, and screw. After fixation, bone density, local tissue reactions, and screw loosening between these two devices at specific periods will be compared.

Time And Place

The clinical study will be conducted at Cipto Mangunkusumo Hospital, Jakarta, Indonesia from September 2019 – April 2020. Surgery will take place at Cleft Craniofacial Center Operating Theatre. It will be conducted by two consultants of craniomaxillofacial surgeons.

STUDY POPULATION

Inclusion Criteria

- Midface fracture with the indication of surgery
- Midface fracture sustained within 2 weeks

Exclusion Criteria

- Comminuted and defect fracture
- Midface fracture on patients with systemic diseases affecting bone healing.
- Midface fracture in children
- Midface fracture in multiple trauma patients with neurological deterioration

Dropout Criteria

- Patient who is unable to complete radiological evaluation after surgery due to lost to follow up or refuse to continue the evaluation will be replaced by another sample
- Patient with signs of bacterial infection either locally or systemically or implant failure are not dropouts, their last data of observation will be included and analyzed (Last-Observation-Carried-Forward (LOCF) method).

METHODOLOGY

Subject Allocation

Subject is the fracture line found on the patient. The surgeon is not blinded on which miniplate is going to use because the miniplate has different characteristic.

Intervention

Pre-operatively

- Patients will sign the informed consent sheet and declare that they want to be enrolled as subjects and obey all the instructions given postoperatively
- The patients will shower with chlorhexidine 4% 27 soap 1 day before surgery
- An empiric antibiotic will be administered 1 hour preoperatively: intravenous injection of Ampicillin Sulbactam 1.5 gr/IV 28 to prevent postoperative infection.

Intra-operatively

- All patients will be treated under general anesthesia.
- After induction of anesthesia, the operating field is disinfected with povidone-iodine
- Draping the patient, exposing only the area of surgery
- Local anesthetic solution with a vasoconstrictor is administered along the incision line area for homeostasis
- Maxillary mandibular fixation is performed to maintain the occlusion
- Midface fracture site approach through an intra-oral or extra-oral incision according to the accessibility at that time and may differ for every patient
- The fractured segment is reduced into proper position using Carroll-Girrard, hook, elevator or Rowe disimpaction forceps.

- The surgeon will received a seal envelope contain an instruction to use locally-made miniplate or existing benchmark miniplate and then it will be bend as desired based on the fracture site contour
- The surgeon will place the miniplate on the fracture site based on AO/CMF point fixation sequence.
- The plate is tapped manually with gentle pressure. The screw is inserted into the hole using a screwdriver and held parallel to the long axis of the drill hole.
- The steps of drilling, tapping and screwing all panel holes are repeated for all screw holes followed by the closure of the incision with usual manner.
- The maxillary mandibular fixation is removed and the jaw is manipulated to evaluate the occlusion and also measure the maximal mouth opening. Forced-duction test is performed when there is a placement of the plate on the orbital rim.
- The maxillary mandibular fixation is maintained for approximately 2 weeks and evaluates once a week during patient visit to the outpatient clinic

Post-operatively

- Intravenous injection of Ampicillin Sulbactam 1.5 gr every 6 hours is given for 1-2 days, then when the patient is discharged it is replaced by Amoxicillin/clavulanic acid 625 mg orally every 8 hours for another 7 days post-operatively
- Intravenous injection of Paracetamol 1 gr every 8 hours is given for 2 days followed by oral tablets 500 mg every 8 hours as needed for another 7 days for pain control
- All patients undergo a non-contrast head CT scan on day one postop as a baseline
- All patients are discharged two days after surgery and instructed to have liquid diet for 2 weeks post-operatively
- Patients will visit the outpatient clinic once a week for 3 weeks. Sign of bacterial infection or local tissue reaction will evaluate by the end of 3rd week
- All patients performed a non-contrast head CT scan at 3 months postoperatively.

Miniplate And Screw Placement

Once a patient lies down on the operating table under general anesthesia, the surgeon will identify the fracture segment. The surgeon will received a seal envelope contain an instruction to use locally-made miniplate or existing benchmark miniplate to be placed on the fracture site according to a predetermined randomization list. The decision where to place the locally made miniplate or existing benchmark miniplate depends on AO/CMF point of fixation sequence.

Assessing Study Results

After completing the procedure, subjects will undergo non-contrast head CT scan evaluation immediately after surgery as a baseline, and by the end of 3rd months post-operation. Afterward, a radiologist consultant as a blinded independent evaluator will assess the bone density score in each subject. A score sheet will be given to the assessor. Subjects will also be instructed to visit the outpatient clinic once a week for 3 weeks post-operatively to evaluate their appearances clinically if there is any sign of bacterial infection or local tissue reaction that will be taken care of by consultants of craniomaxillofacial surgeons.

Bone Density

Bone density of each subject will be recorded in Hounsfield Unit (HU). The bone density score of each subject will be noted and scores between the two brands will be compared. The scores will be evaluated by a radiologist consultant and act as an independent evaluator after the subject has completed all their Head CT evaluation.^{29, 30}

[figure not shown]
Screw Loosening

Screw loosening will be recorded, whether it is present or not. It will be evaluated by a radiologist consultant after the subject completed all their Head CT evaluation.

Tissue reaction

Local tissue reactions such as edema, bacterial infection, or any other signs of the inflammation process, will be recorded by the end of the 3rd week during patient's visit outpatient clinic. It will be evaluated by consultants of craniomaxillofacial surgeons and.

Research Protocol

DATA ANALYSIS AND DATA PRESENTATION

Data on bone density are quantitative, all scores from points of evaluation group will be collected, and scores for the dependent variables between groups will be statistically compared using independent t-test or Mann Whitney test depending on the distribution of the data is normal or not. Other findings will be presented using descriptive statistics.

Table 2. Dummy table of bone density (HU) in group I (Locally-made miniplate and screw) versus group II (existing benchmark miniplate and screw) at different observation periods.

Time (Postop)	Group I (Mean ±SD)	Group II (Mean ±SD)	p-Value*
Bone Density			
Immediately post op			
Three months post op			

*Statistically significant difference versus baseline reading if p-value ≤ 0.05 HU=Hounsfield unit.

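### Patients lost or refusing after plating are replaced, and an infected or failed patient with no later CT has the day-1 HU carried forward as the 3-month primary outcome

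*Combined protocol and SAP*

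**What the plan says.** All references are to the combined protocol and SAP.

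- **Dropout Criteria, first bullet.** A patient who cannot complete radiology after surgery "due to lost to follow up or refuse to continue the evaluation will be replaced by another sample".
- **Dropout Criteria, second bullet.** Patients with bacterial infection or implant failure do not count as dropouts; "their last data of observation will be included and analyzed (Last-Observation-Carried-Forward (LOCF) method".
- **Intra-operatively; Miniplate And Screw Placement.** The surgeon receives the sealed envelope in theatre, and the plate is used "according to a predetermined randomization list".
- **Post-operatively.** "All patients undergo a non-contrast head CT scan on day one postop as a baseline"; "All patients performed a non-contrast head CT scan at 3 months postoperatively". Assessing Study Results and Table 2 give the same two time points for density.
- **Subject Allocation.** "Subject is the fracture line found on the patient". Both dropout rules, however, are written for the patient.
- **Miniplate And Screw Placement.** "The decision where to place the locally made miniplate or existing benchmark miniplate depends on AO/CMF point of fixation sequence". This suggests, without stating it, that one patient may carry both plates.
- **Table 3.** The dummy headings show 60 per group.

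**The concern.** The hypothesis is non-inferiority, and the 3-month HU is the only scheduled post-baseline reading of the primary outcome. Two rules act on it after allocation.

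Replacement removes patients who have been randomised and plated and substitutes others. What remains is a comparison of completers. The text does not say whether a replacement takes the same allocation or a new envelope. A table filled back to 60 per group could also hide how many were lost and from which group.

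LOCF normally carries a recent follow-up value forward. With only two scheduled CTs, the sole value available for a patient without the second is the baseline. The patients treated this way are those with infection or failure, in whom no change from day 1 is hardest to assume. If the two plates differ in how often this happens, or in how far the truth lies from day 1, the comparison shifts. In a non-inferiority trial a shift that flatters the local plate matters most.

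**Working it through.** **1. The plan's own figure.** The 60 per group has no stated derivation and cannot be reproduced: the supplied text gives no SD, margin, power or dropout rate. For scale only, at one-sided 0.025 with no true difference, it supports a margin of (1.96 + 0.84) × √(2/60) = 0.51 SD at 80% power and (1.96 + 1.28) × √(2/60) = 0.59 SD at 90%. The standard error of the difference is √(2/60) = 0.183 SD for independent lines; no within-patient correlation is given.

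**2. When the rules act.** Envelope in theatre, then plating, then day-1 CT, then 3-month CT. Loss or refusal after surgery is therefore loss after randomisation. If the 3-month CT is missing and no unscheduled CT exists, the last HU is day 1. If the 3-month CT exists, LOCF is not needed.

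**3. LOCF shift (all inputs assumed).** Let f be the share of lines carried forward and d the distance, in SD, by which their true 3-month HU lies below day 1. Each such line is overstated by d, so local minus benchmark shifts by f_L·d_L − f_B·d_B. With no patient carrying both plates:

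| f local / benchmark | d local / benchmark | Shift (SD) | In standard errors |
|---|---|---|---|
| 0.10 / 0.05 | 0.5 / 0.5 | 0.025 | 0.14 |
| 0.10 / 0.05 | 1 / 1 | 0.05 | 0.27 |
| 0.10 / 0.10 | equal | 0 | 0 |
| 0.10 / 0.10 | 1 / 0.5 | 0.05 | 0.27 |
| 0.10 / 0.05 | 0.5 / 1 | 0 | 0 |
| 0.05 / 0.10 | 0.5 / 0.5 | −0.025 | −0.14 |
| 0.10 / 0.05 | −0.5 / −0.5 | −0.025 | −0.14 |

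The fifth row shows that the products must differ; a difference in share or distance alone is not enough. Under a wider assumption of 20% versus 5%, the shift runs from 0.15 × 0.5 = +0.075 SD to 0.15 × (−1) = −0.15 SD. The latter is 0.82 standard errors, and applies if failed lines in fact gained 1 SD.

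**4. Patients with both plates.** One head CT covers every line in a patient, so a missed CT affects both groups. If a share w of lines sits in such patients, in equal numbers per plate and with equal d, only the remaining 1 − w contributes. At w = 0.5 the 0.025 to 0.05 SD above becomes 0.0125 to 0.025 SD; at w = 1 it is 0. If d differs between the two lines of one patient, a shift remains, as in the fourth row.

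**5. Loss and refusal.** If lost lines lie d below retained ones, completers overstate a group by q·d, where q is the share lost. The shift is (1 − w)(q_L − q_B)·d, with q the loss rates among single-plate patients. For 20% versus 10% and d = 0.5 it is 0.05, 0.025 and 0 SD at w = 0, 0.5 and 1. Substitution does not change this if replacements resemble completers.

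**6. Would model-based imputation do better?** Assume healed lines gain 0.5 SD and failed lines lose 0.5 SD.
- *Failure 20% versus 10%, half of failures without a CT.* LOCF: (0.10 − 0.05) × 0.5 = 0.025 SD. Imputing from observed lines while ignoring failure status gives a local mean of (0.8 × 0.5 − 0.1 × 0.5)/0.9 = 0.389, an error of 0.10 × 0.889 = 0.0889. The benchmark mean is (0.9 × 0.5 − 0.05 × 0.5)/0.95 = 0.447, an error of 0.05 × 0.947 = 0.0474. The shift is 0.0415 SD, worse than LOCF. With failure status included it is 0, if failed lines with and without a CT are alike.
- *Failure 10% versus 5%, all without a CT.* LOCF 0.025 SD; ignoring status, (0.10 − 0.05) × 1 = 0.05 SD; a status effect cannot be estimated.

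**7. Delta scale.** Lowering imputed values for 10% of local lines by 0.5 to 1 SD moves the difference by 0.05 to 0.10 SD.

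**The case against.** The strongest reply is that the rules are milder than they look. The 3-month CT is scheduled for all patients, infected ones included, so LOCF matters only when that scan is missed and no unscheduled scan was taken. Both rules apply to both plates, and patient-level loss in anyone carrying both draws the shares together. The main illustrative shifts are at most 0.27 standard errors. Replacement adds nothing to completers-only bias, the 60 is only a dummy-table heading, and nothing prevents losses from being reported. Imputation that ignores failure status can do worse than LOCF. All of this stands: it limits the size of the point and shapes the remedy. It does not restore the randomised set or make a baseline scan a 3-month result.

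A reader might infer more, in three ways.
- *That the plan leaves open whether an infected or failed patient who is then lost is replaced or carried forward.* The second bullet follows the replacement rule directly and says such patients are not dropouts. The natural reading keeps them. That precedence is implied, not written out, and it cannot help a patient whose failure is never seen because they stop attending.
- *That the rules favour the local plate.* The sign reverses with the assumed shares or distances, and the documents fix neither.
- *That the 2-month row in Table 3 supplies an intermediate HU.* It concerns screw loosening, and no 2-month CT is scheduled.

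**Conclusion.** The point holds in this form and should be fixed. Replacement after randomisation is a stated rule. LOCF of the day-1 HU follows by deduction from the two-scan schedule, for infected or failed patients with no later CT. It concerns HU only.

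The size rests wholly on assumption: 0.025 to 0.05 SD in the base illustration with no shared patients, less where patients carry both plates with equal distances, and from +0.075 to −0.15 SD under wider assumptions. These are modest against a standard error of 0.183 SD. Without a stated margin or expected rates they cannot be shown to be negligible. The case rests on the principle of keeping the randomised set in a non-inferiority comparison, and on the low cost of repair, more than on demonstrated impact.

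**What to change.** - **Randomised set.** Keep every randomised line in its allocated group. Extra patients may be enrolled but not substituted. Report losses and refusals by group, with timing.
- **3-month HU.** Do not carry the day-1 HU forward. For infected or failed patients use the 3-month CT already scheduled.
- **Missing 3-month CT.** Make a delta-adjusted sensitivity analysis the main safeguard, lowering local-plate values over a range stated in advance and judged against the non-inferiority margin once one is given. Use multiple imputation or a mixed model (day-1 HU, site, plate, infection or failure status, lines within patient) only if enough failures have an observed 3-month CT to estimate the status effect.
- **Precedence.** Say explicitly that an infected or failed patient who is then lost or refuses is kept, not replaced.

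As a separate minor point, the 2-month loosening row in Table 3 and the CT schedule must be reconciled.

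The cost is protocol and SAP wording, a little more analysis and possibly fewer than 60 lines per group with both CTs. No extra visits or scans are needed.

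### The unit is the fracture line, but HU is compared with tests that ignore the patient; if patients contribute several lines, the test's error rate depends on an allocation unit the plan does not state

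*Combined protocol and SAP*

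**What the plan says.** **Unit.** Methodology, Subject Allocation: "Subject is the fracture line found on the patient".

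**Outcome and test.** Bone Density: "The bone density score of each subject will be noted and scores between the two brands will be compared". Data Analysis and Data Presentation says the scores will be "statistically compared using independent t-test or Mann Whitney test", the choice depending on normality. The supplied text has no patient term, pairing, averaging within patient or one-line-per-patient rule.

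**Allocation.** Miniplate And Screw Placement can be read both ways. It begins at the patient: "Once a patient lies down on the operating table under general anesthesia, the surgeon will identify the fracture segment", and a sealed envelope follows. But the plate is "to be placed on the fracture site according to a predetermined randomization list", which points to the line. It then adds: "The decision where to place the locally made miniplate or existing benchmark miniplate depends on AO/CMF point of fixation sequence".

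**Other uses of the word subject.** Pre-operatively: "Patients will sign the informed consent sheet and declare that they want to be enrolled as subjects". Assessing Study Results: "Subjects will also be instructed to visit the outpatient clinic once a week for 3 weeks post-operatively". In both places a subject is a person. Table 3 heads its columns with n=60 per group and does not say whether that counts people or lines.

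**The concern.** Both planned tests treat every score as independent. Lines in one face share the patient's bone, healing, operation and CT scans, so their HU values are likely to be correlated. If a patient supplies more than one line, the standard error of the plate comparison is then wrong in a direction set by the allocation:

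- **One plate type per patient.** Patient-to-patient variation falls between the groups. The standard error is too small, the interval too narrow, and a difference between plates is declared too often.
- **Both plates balanced within patient.** That variation cancels from the difference, but the test still counts it. The interval is too wide and the test conservative.
- **Lines randomized without regard to patient.** The test is valid, but less precise than one that uses the patient.

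As written, two statisticians could analyse the same data differently, and the reader could not tell which standard error is right.

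**Working it through.** **Inputs from the documents.** 60 per group (Table 3), taken here as lines; significance at 0.05 (Table 2 footnote), taken as two-sided. The supplied text gives no SD, effect size, margin or power from which the 60 could be reproduced.

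**Assumptions, because the documents give neither figure.** Lines per patient m = 2 to 4; intra-patient correlation ICC = 0.1 to 0.5. Results are in SD units.

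**Formulas.** With independent lines, the variance of the difference is 2/60 and the 95% half-width is 1.96 × √(2/60) = 0.36 SD. The true variance is this multiplied by a factor V:

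- one plate type per patient: V = 1 + (m − 1) × ICC, effective n = 60/V;
- plates balanced within patient, m even: V = 1 − ICC;
- m = 3 with 2:1 and 1:2 splits: V = 1 − (2/3) × ICC.

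The true type I error of the plain test is about 2 × (1 − Φ(1.96/√V)). For example, m = 2 and ICC 0.3 with one plate type gives V = 1.3, 1.96/√1.3 = 1.72, error 0.086 and effective n 60/1.3 = 46.

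**Type I error of the plain t-test** (formula / simulation of 20,000 trials per cell, 120 lines):

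| m | ICC | One plate type per patient | Effective n per group | Balanced within patient |
|---|---|---|---|---|
| 2 | 0.1 | 0.062 / 0.059 | 54.5 | 0.039 / 0.041 |
| 2 | 0.3 | 0.086 / 0.086 | 46 | 0.019 / 0.019 |
| 2 | 0.5 | 0.110 / 0.110 | 40 | 0.006 / 0.007 |
| 3 | 0.1 | 0.074 / 0.073 | 50 | 0.043 / 0.046 |
| 3 | 0.3 | 0.121 / 0.120 | 37.5 | 0.028 / 0.030 |
| 3 | 0.5 | 0.166 / 0.172 | 30 | 0.016 / 0.018 |
| 4 | 0.1 | 0.086 / 0.084 | 46 | 0.039 / 0.041 |
| 4 | 0.3 | 0.155 / 0.157 | 32 | 0.019 / 0.020 |
| 4 | 0.5 | 0.215 / 0.228 | 24 | 0.006 / 0.007 |

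Repeat simulations put the largest cell between 0.216 and 0.228. With independently randomized lines the simulated error was 0.046 to 0.051 in every cell. With m = 1 it was 0.049 to 0.052.

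**Mann-Whitney.** The pattern is the same: 0.082 to 0.217 with one plate type per patient (ICC 0.3 to 0.5), and 0.048 to 0.051 with independent lines. With skewed data it was 0.004 to 0.024 when plates were balanced.

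**Interval width.** The plain test gives 0.36 SD in each case. Under a random-intercept model, one plate type per patient needs 0.415 SD (m = 2, ICC 0.3) to 0.587 SD (m = 4, ICC 0.5). Balanced plates at m = 2 need only 0.304 SD (ICC 0.3) or 0.257 SD (ICC 0.5).

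**Power at 0.5 SD, ICC 0.3 to 0.5, plain t-test against mixed model.** Balanced, m = 2: 82–85% against 90–97%. Independent lines: 77–78% against 81–93%.

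**Does the remedy hold?** The random-intercept model kept type I error at 0.046 to 0.054 over 27 cells (three allocations, m = 2 to 4, ICC 0.1 to 0.5). Patient-clustered standard errors gave 0.046 to 0.056 in the same cells. A separate run that included unequal numbers of lines and mostly single-line patients gave 0.044 to 0.058.

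**The case against.** The strongest objection is to the premise. No sentence says that a patient contributes several lines. Much of the wording is singular (the fracture line, the fracture segment, one envelope), and the content of the AO/CMF fixation sequence is not in the documents. A page and a figure are also missing from the supplied text. This stands: several lines per patient is an inference. It is a reasonable one, because naming the line as the unit has little purpose if each patient has one, and because the text speaks of deciding where each type of plate goes.

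Second, a reader might infer that type I error is inflated. The documents do not support that as a general statement. Placing the unit under Subject Allocation and tying the plate to the fracture site by a list arguably favours line-level randomization, where the error is about nominal. Inflation needs one plate type per patient.

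Third, a reader might infer that non-inferiority would be falsely claimed. The visible plan gives no margin and no confidence-interval rule. It plans a difference test, so inflation there means a false difference between plates. No rate of false non-inferiority claims can be attached to this plan.

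Fourth, the power loss is relative. Sixty against 60 independent observations give 77.5% power at 0.5 SD, and the plain test reaches 77–78% with independent lines and 81–86% with balanced plates. What is lost is the gain that a patient-level analysis would bring. That is correct, and it limits the weight of those two cases.

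**Conclusion.** The point holds conditionally and should be fixed. The plan names the fracture line as its unit, uses tests that assume independent observations, and neither limits a patient to one line nor accounts for the patient.

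If patients contribute several lines, and for the assumed m of 2 to 4 and ICC of 0.1 to 0.5, the nominal 5% test has type I error of:

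- about 0.06 to 0.23 with one plate type per patient;
- about 0.05 with independently randomized lines (valid but less precise than a mixed model);
- about 0.007 to 0.046 with plates balanced within patient (conservative, interval too wide).

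With one line per patient there is no error. Confidence is medium, because lines per patient, ICC and the allocation unit are not given. Nor do the figures show that the Mann-Whitney test is wrong in every case: it is sound with one line per patient or with lines randomized independently of patient.

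**What to change.** 1. State the allocation unit (patient or line), how many lines a patient may contribute, and whether n=60 counts lines or patients.
2. If every patient contributes exactly one line, say so. The planned tests then need no change on this account.
3. Otherwise analyse 3-month HU with a linear mixed model (plate as fixed effect, random intercept for patient) or with patient-clustered standard errors. The clustered version is valid but recovers little precision when lines are randomized independently: power at 0.5 SD was 75–78%. Report the plate difference with its 95% CI, and the number of patients as well as lines per group.
4. If HU is clearly non-normal, use a patient-level bootstrap or a permutation test that matches the allocation unit: whole patients, within patient, or lines. Keep the ordinary Mann-Whitney test only for one line per patient or for lines randomized independently of patient.

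**Cost.** SAP wording, a slightly more complex model and a patient identifier for each line. No new data are needed if lines are already linked to patients. The effective sample size may prove to be below 60 per group.

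### Two rules decide which plate goes on which fracture line, and no envelope is tied to a line, so confounding of plate with site cannot be ruled out

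*Combined protocol and SAP*

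**What the plan says.** Subject Allocation defines the unit: "Subject is the fracture line found on the patient". It adds: "The surgeon is not blinded on which miniplate is going to use because the miniplate has different characteristic".

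Miniplate And Screw Placement gives the steps in theatre. It begins: "Once a patient lies down on the operating table under general anesthesia, the surgeon will identify the fracture segment". The surgeon then receives a sealed envelope naming one of the two plates, "to be placed on the fracture site according to a predetermined randomization list". The next sentence is: "The decision where to place the locally made miniplate or existing benchmark miniplate depends on AO/CMF point of fixation sequence".

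The Intra-operatively list gives reduction of the fracture, then the envelope, then bending of the plate to the contour of the site, and then: "The surgeon will place the miniplate on the fracture site based on AO/CMF point fixation sequence".

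Under Data Analysis and Data Presentation, bone density in the two groups is to be "statistically compared using independent t-test or Mann Whitney test depending on the distribution of the data is normal or not". No site term or stratification by site is described.

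**The concern.** Because the line is the unit, randomisation protects the comparison only if the list alone decides which plate a given line receives, and the line is fixed before the plate is known. The Placement section names the list as the rule. It then names the AO/CMF sequence as the rule for where each brand goes. It does not say how the two combine, how many envelopes are opened per patient, or whether the lines are listed before the first envelope is opened.

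This matters most in a patient with several fracture lines. If plate and site became linked, a difference in Hounsfield units between sites would appear as a difference between plates, or would hide one. The study aims to show that the local plate is not inferior on bone healing, so a shift in either direction could change the conclusion. The blinded radiologist protects the measurement but not the pairing of plate and line.

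**Working it through.** The documents state no figure on this point to reproduce. The check sets the wording side by side and then illustrates the size.

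**1. Order of steps.**

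| Step | Miniplate And Screw Placement | Intra-operatively list |
|---|---|---|
| Before the envelope | Fracture segment identified | Segment reduced |
| Envelope | Names a plate; randomisation list governs | Names a plate; plate then bent to the site |
| After the envelope | AO/CMF sequence decides where each brand goes | Plate placed by AO/CMF sequence |

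Identification comes before the envelope. Neither section says that one identified line, among several, is committed to the next envelope.

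**2. What each reading implies.**

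- *The sequence sets the order of fixation, and each line in turn takes the next envelope.* The list alone sets the plate. A simulation of 4,000 trials with a site difference of 0.5 SD gave a mean bias of −0.002 SD, in effect zero.
- *The plate is known first, and a line is then chosen.* With an assumed 70/30 preference and the same site difference, the simulated bias was 0.203 SD. The formula below gives (0.70 − 0.30) × 0.5 = 0.20.
- *A given plate always goes to a given position in the sequence.* To the extent that position determines site, the bias approaches the whole site difference.

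The text confirms none of the three and excludes none.

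**3. Illustration of size.**

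Inputs from the documents:
- 60 per group, from the column heads of dummy Table 3, taken here as lines.
- A 0.05 level, from the footnote to Table 2. Its sidedness is not stated, so two-sided is assumed.

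Assumed inputs, because the documents give no Hounsfield values by site:
- Two site types differing by D within-site SDs.
- A share p = 0.60 of one plate group, and 1 − p = 0.40 of the other, on the denser site.
- Independent lines; clustering within patients is ignored.

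Formulas:
- Bias = (p − (1 − p)) × D = (2p − 1) × D
- Variance per line = 1 + D² × p × (1 − p)
- SE = √(2 × variance / 60)
- Chance of p ≤ 0.05 with no plate effect = Φ(bias/SE − 1.96) + Φ(−bias/SE − 1.96)

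| D | Bias (SD) | Variance | SE | Bias/SE | Chance of p ≤ 0.05 |
|---|---|---|---|---|---|
| 0.5 | 0.2 × 0.5 = 0.10 | 1 + 0.25 × 0.24 = 1.06 | 0.188 | 0.53 | 8.3% |
| 1.0 | 0.2 × 1.0 = 0.20 | 1 + 1 × 0.24 = 1.24 | 0.203 | 0.98 | 16.6% |

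With an even split (p = 0.50) the bias is 0 and the rate is 5%. The sign depends on which plate falls on the denser site, which the documents do not indicate.

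**The case against.** The strongest answer is that the wording is loose but the procedure may be sound. The segment is identified, and in the other section reduced, before the envelope appears. The plate is bent to the contour of a site, which suggests a site already settled. On that view the AO/CMF sequence sets only the order of work, the list sets the plate, and no systematic bias arises. This stands as a possible reading. A reader might infer from the order of the surgical steps that the envelope is opened before the line is chosen. The documents do not support that as fact: any randomised plate is placed after it is named, and the Placement section puts identification first.

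The benign reading still has to set aside what the AO/CMF sentence says, since its subject is where each brand goes. Identifying a segment also does not commit one line among several to the next envelope.

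Other points carry partial weight:

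- Baseline CT values by group are planned for Table 2, so a large imbalance driven by site might show. That helps detection but does not adjust the three-month comparison.
- A site term could remove the kind of partial imbalance illustrated above. None is planned. It could not separate plate from site if position fixed the plate, nor correct the choice of an easier line within one site type.
- The two harmful mechanisms are alternatives. A strict sequence leaves no free choice of line, and free choice means that the sequence does not fix the plate. The text does not say which, if either, applies.
- The Research Protocol heading has no content under it in the text available, so envelope details may exist elsewhere. The AO/CMF sentence would still need rewording.

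**Conclusion.** The concern holds as a conflict in the allocation rule, not as evidence of bias. The unit is the line, the surgeon is unblinded, two rules govern the pairing of plate and line, no envelope is tied to a line, and the planned test has no site term. Confounding of plate with site therefore cannot be ruled out in patients with several lines.

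The illustrated bias of 0.10 to 0.20 SD, about 0.5 to 1.0 standard errors, rests wholly on the assumed split and site difference and is not an estimate. A more extreme split would give larger figures, but the documents support no particular split. A reader might also infer that any bias favours the local plate; nothing in the documents sets its direction. The effect on a non-inferiority conclusion cannot be calculated, because the text available states no margin.

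**What to change.** Reword Miniplate And Screw Placement, and the matching step in the Intra-operatively list, to give one order of steps:

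1. Before any envelope is opened, the surgeon lists and numbers the study fracture lines on the case form, in their existing AO/CMF order.
2. One sequentially numbered envelope is opened per listed line, in that order, and the plate it names is used on that line.
3. The AO/CMF sequence sets only the order of fixation; the randomisation list alone sets the plate.
4. Line number and site are recorded, so that the distribution of plates over sites can be reported.

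The cost is protocol wording, one extra entry on the case form and a small amount of theatre time. No change to the clinical fixation sequence is proposed. The step has to be in place before surgery, because line-level randomisation that has been lost cannot be recovered in the analysis.
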